5.4. Rationale for Selection of Dose

The current olaratumab dose-selection strategy for this study is based on the integrated safety, efficacy, and PK data for olaratumab across previous Phase 1 and Phase 2 studies.

In 2 Phase 1 dose-escalation trials (Studies I5B-IE-JGDC and I5B-IE-JGDF) and in the 2 Phase 2 monotherapy studies (Studies I5B-IE-JGDE and I5B-IE-JGDH), single-agent olaratumab has consistently been well tolerated, with no dose-limiting toxicities observed up to a dose of 20 mg/kg administered every 2 weeks and up to a dose of 15 mg/kg administered on Days 1 and 8 of a 21-day cycle. When used in combination with liposomal doxorubicin in Study I5B-IE-JGDA (olaratumab dose of 20 mg/kg every 2 weeks), and with paclitaxel plus carboplatin in Study I5B-IE-JGDB (olaratumab dose of 15 mg/kg Days 1 and 8 every 3 weeks), a higher rate of toxicities such as neutropenia and infections was observed versus the comparator agents. In Study JGDG, an increase in neutropenia and mucositis, but not in neutropenic sepsis or febrile neutropenia, was observed for olaratumab plus doxorubicin compared with single-agent doxorubicin. Overall, these toxicities are consistent with the toxicity profile of the combination agents used, and are considered monitorable and acceptable for the patient populations studied.

Based on an exposure-response analysis of data from Study JGDG, an olaratumab loading dose of 20 mg/kg on Day 1 and Day 8 of Cycle 1 was incorporated into Study I5B-MC-JGDJ (JGDJ), an ongoing randomized Phase 3 trial of doxorubicin plus olaratumab versus doxorubicin plus placebo in patients with advanced or metastatic STS. The goal of this dosing refinement was to decrease the time patients achieved steady state concentrations of olaratumab.

Study JGDM will consist of an initial cycle of olaratumab monotherapy (Cycle 1) administered on Day 1 and Day 8 of a 21-day cycle using a dose of 20 mg/kg. This dose is consistent with the loading dose used in Study JGDJ, and is anticipated to provide olaratumab concentrations optimal for testing olaratumab tumor and CTC biomarker effects during Cycle 1.

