7.2.3. Dose Modifications

7.2.3.1. Dose Delays, Modifications, and Discontinuations

After treatment has been initiated, in order to start the next cycle, the following criteria must be fulfilled:

- ANC $\geq 1.0 \times 10^3/\mu\text{L}$ (1000/ μL ; $\geq 1.0 \times 10^9/\text{L}$)

Note that in order to administer single-agent olaratumab on Day 8, ANC must be $\geq 750/\mu\text{L}$; $\geq 0.75 \times 10^9/\text{L}$. If the ANC is $< 750/\mu\text{L}$, the Day 8 administration of olaratumab may be delayed for a maximum of 7 days. If the ANC level has not increased to $\geq 750/\mu\text{L}$ within 7 days, then the Day 8 olaratumab dose in that cycle should be skipped and dosing resumed on Day 1 of the following cycle if criteria for dosing are met. If all dosing criteria are met, a delay or omission of the Day 8 olaratumab dose should not result in a delay of the Day 1 olaratumab dose of the following cycle.

- Platelets $\geq 100 \times 10^3/\mu\text{L}$ (100,000/ μL ; $\geq 100 \times 10^9/\text{L}$)
- Hemoglobin ≥ 8 g/dL
- Creatinine clearance ≥ 45 mL/min (refer to [Attachment 7](#) for the Cockcroft-Gault formula)
- Proteinuria ≤ 1000 mg in 24 hours (if routine urinalysis indicates $\geq 2+$ proteinuria) (to be performed every other cycle)

- Total bilirubin below ULN
- AST and ALT $\leq 3.0 \times$ ULN, or $\leq 5 \times$ ULN if the transaminase elevation is due to liver metastases
- Olaratumab-related AEs that are NCI-CTCAE Version 4.0 Grade <2 or equivalent severity to baseline

Delays:

In general, dose delays of 1 study drug (olaratumab or doxorubicin) due to toxicity guidances outlined in Sections 7.2.3.1.1 and 7.2.3.1.2 will not necessitate delays of the other study drug.

Treatment may be delayed for up to 21 days (1 equivalent cycle) to allow a patient sufficient time for recovery from study drug-related toxicity. If a patient does not recover from the toxicity within 42 days (2 equivalent cycles) from Day 1 of the previous treatment cycle, then the patient must be discontinued from study therapy.

Any procedure or sample collection whose timing is related to olaratumab dosing is to be completed according to when the olaratumab dose was actually administered, not when that dose was expected to occur. Samples whose adjusted timing would fall outside of the treatment cycle duration due to dose delay may be omitted.

Dose Modifications:

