7.2.3.1.2. Doxorubicin

7.2.3.1.2.1. Hematologic Toxicity

Doxorubicin will not be administered after the initial dose if the patient's ANC is <1000 cells/ μL or if the platelet count is $<100,000$ cells/ μL . When necessary, the next treatment cycle should be delayed until the ANC is ≥ 1000 cells/ μL and the platelet count is $\geq 100,000$ cells/ μL and nonhematologic toxicities have resolved. For patients who experience \geq Grade 3 neutropenic fever or infection or Grade 4 neutropenia without fever lasting more than 1 week, doxorubicin should be reduced to 75% of the starting dose (that is, to approximately 60 mg/ m^2). If a patient experiences a second incidence of neutropenic fever/infection or has another episode of Grade 4 neutropenia lasting >1 week, then a second dose reduction to 45 mg/ m^2 will be necessary. Therapeutic and prophylactic use of pegfilgrastim (Neulasta[®]) or other G-CSFs will be allowed per current American Society of Clinical Oncology (ASCO; Smith et al. 2006) and National Comprehensive Cancer Network (NCCN) guidelines (NCCN 2014). For patients with Grade 4 ANC without fever/infection lasting less than 1 week, retreatment will be allowed at the investigator's discretion with the full dose of doxorubicin (75 mg/ m^2) with recommended use of

G-CSFs per current ASCO guidelines (Smith et al. 2006). See [Table JGDM.4](#) for doxorubicin dose modification for neutropenia.

Table JGDM.4. General Guidelines for Doxorubicin Dose Modification Due to Neutropenia

Toxicity	Required Dose Modification
ANC <1000 cells/ μ L	No doxorubicin administered; treatment cycle delayed.
At pretreatment:	
If Grade ≥ 3 neutropenic fever/infection has occurred	Approximately 60 mg/m ² doxorubicin.
If Grade 4 neutropenia lasting longer than 1 week has occurred	Approximately 60 mg/m ² doxorubicin.
Grade 4 ANC without fever/infection	Retreatment with doxorubicin at full dose at investigator's discretion with recommended use of prophylactic G-CSFs.
Second incidence of either:	
1) Grade ≥ 3 neutropenic fever/infection	Second dose reduction to 45 mg/m ² .
2) Grade 4 neutropenia lasting longer than 1 week	

Abbreviations: ANC = absolute neutrophil count; G-CSF = granulocyte colony-stimulating factor.

7.2.3.1.2.2. Cardiovascular Toxicity

Cardiotoxicity is a recognized risk of doxorubicin that increases with higher cumulative drug exposure. Cardiac monitoring is conducted by a combination of monitoring of clinical parameters, ECG, and ECHO/MUGA scans.

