	6.1	Vital Signs	X	X	X	X	Vital signs include blood pressure, pulse, and temperature. During the Observation Period (initial 2 cycles of olaratumab therapy), collect vital signs 3 times: 
 • within 15 minutes (+5 minutes) prior to olaratumab infusion • within 1 hour (+5 minutes) after completion of the olaratumab infusion • within 1 hour (+5 minutes) after completion of the doxorubicin infusion. Thereafter (Cycles 3+), obtain vital signs 2 times: within 15 minutes (+5 minutes) prior to olaratumab infusion within 1 hour (+5 minutes) after completion of the doxorubicin infusion.		
Lab/ Diagnostic Tests	Attachment 2	Hematology	X	X	X	X	Laboratory assessments may be done within 7 days prior to D1 and D8 of each cycle. See Attachment 2 for details. Testing will be performed locally for patient management and centrally for analysis purposes.		
	Attachment 2	Serum Chemistry	X		X		Laboratory assessments may be done within 7 days prior to D1 of each cycle. See Attachment 2 for details. Testing will be performed locally for patient management and centrally for analysis purposes.		
	Attachment 2	Coagulation Profile	X		X		Perform on D1 every other cycle or as clinically indicated. See Attachment 2 for details. Testing will be performed locally only.		
	Attachment 2	Urinalysis	X		X		Laboratory assessments may be done within 7 days prior to D1 of every other cycle or as clinically indicated. Includes a routine UA, and, if clinically indicated, a microscopic analysis. If routine analysis indicates >2+ proteinuria, then a 24-hour urine must be collected and must demonstrate ≤1000 mg of protein in 24 hours. Testing will be performed locally only.		
	Attachment 2	Pregnancy Test	X		X		Serum β-HCG or urine pregnancy test on D1 of every cycle or per local practice (whichever is of shorter duration). If a pregnancy test performed on D1 of the cycle is positive, confirm with a serum or urine pregnancy test (pregnancy test results are not recorded on the eCRF). If results are positive, the investigator is to consult with the Lilly CRP. Testing will be performed locally only.		
	8.2.2 Attachment 4	PK Samples	See Attachment 4 for specific time points					Whole blood samples collected for olaratumab serum PK measurements.	

Procedure Category	Protocol Section	Procedure	Study Period				Treatment Period				Comments

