	8.1.3.1	ECG	X			X				Twelve-lead ECGs are to be collected on Day 1 of monotherapy Cycle 1 and on Day 1 of combination therapy Cycles 2-7. Patients who stop doxorubicin prior to Cycle 7 will undergo the same cardiac monitoring assessment. ECGs will be read locally and measurements will be electronically submitted to a central vendor.	
	8.1.3.2	Echocardiogram or MUGA							X	Echocardiograms or MUGA scans must be performed at the end of combination therapy Cycles 5 and 7 and when clinically indicated. After Cycle 7, (resting LVEF ≥50%), perform echocardiograms or MUGA at the 30-day follow-up visit. Patients who stop doxorubicin prior to Cycle 7 will undergo the same cardiac monitoring assessment. For patients with LVEF <50% or other cardiac dysfunction, perform more frequently, if clinically indicated.	
	8.2.3.3	PET Scan				X				Mandatory PET scan must be collected up to 3 days prior to the first dose of C2D1. PET scans will be read locally by the investigator and sent to a central vendor where the images will be stored.	

Procedure Category	Protocol Section	Procedure	Treatment Period				Comments	
			Study Period		Treatment Period			
					Olaratumab Monotherapy	Combination Therapy Olaratumab + Doxorubicin		
			Cycle (21-day cycle ±3 days)		1			2-7
Relative Day within Cycle (± 3 days)		1 ^{ab}	8 ^a	1 ^a	8 ^{ab}			
Efficacy Assessment	Attachment 8	Imaging Studies (CT/MRI) Tumor Assessments (according to RECIST v1.1)			X		Imaging studies and tumor assessments are to be obtained every 6 weeks (up to 7 days before), irrespective of treatment cycles as calculated from enrollment, until documented progression for patients with CR, PR, or SD, and/or for patients who have discontinued study treatment due to toxicity or reasons other than PD. Refer to Attachment 8 for details. CT/MRI scans will be read locally and a scan will also be sent for storage at a central vendor.	
Adverse Events Collection/CTCAE Grading	8.1.2	Toxicity Assessment	X	X	X	X	All AEs considered at least possibly related to study treatment will be followed until resolution, stabilization, or return to baseline, or until deemed irreversible.	
Concomitant Therapy	7.5	Concomitant Medications	X	X	X	X	Concomitant medications will be recorded throughout the treatment period, including those taken during the 30 days after the last dose of all study treatment.	

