Premedication	7.2.2	Administer premedication prior to olaratumab treatment	X	X	X	X	Premedicate all patients with the following medications (or equivalent): a histamine H1 antagonist (eg, diphenhydramine) and dexamethasone intravenously 30–60 minutes prior to the olaratumab doses on Days 1 and 8 of Cycle 1. For subsequent cycles, premedicate all patients with a histamine H1 antagonist (eg, diphenhydramine) intravenously 30-60 minutes prior to each dose of olaratumab.	
	7.2.2	Administer dexrazoxane prior to doxorubicin			X		Dexrazoxane is recommended for all patients receiving 5 or more cycles of doxorubicin.	
Study Treatment	7.1.2	Administer olaratumab	X	X	X	X	Administer through completion of Cycle 7 or until PD, surgical resection, unacceptable toxicity, death, or other withdrawal criteria are met.	
	7.1.3	Administer doxorubicin			X		Administered to all patients during combination therapy for up to a maximum of 6 cycles (Cycles 2-7) (unless previous unacceptable toxicity).	
Patient Disposition			X		X		At the time that the patient is discontinued from any component of the study treatment or study participation, information regarding the patient status will be collected.	

Abbreviations: β -HCG = beta human chorionic gonadotropin; AE = adverse event; BSA = body surface area; C = cycle; CR = complete response; CRP = clinical research physician; CT = computed tomography; CTCAE = Common Terminology Criteria for Adverse Events; D = day; DNA = deoxyribonucleic acid; ECG = electrocardiogram; ECOG = Eastern Cooperative Oncology Group; eCRF = electronic case report form; IRR = infusion-related reaction; LVEF = left ventricular ejection fraction; MRI = magnetic resonance imaging; MUGA = multi-gated acquisition; PD = progressive disease; PET = positron emission tomography; PK = pharmacokinetic; PR = partial response; RECIST = Response Evaluation Criteria in Solid Tumors; SD = stable disease; UA = urinalysis.

- a Study procedures will be performed prior to study drug administration, except where noted (such as vital signs). In case of dose interruption, these evaluations will also be done at minimum frequency every 21 days (± 3 days).
- b Relative day within each cycle (≤ 3 days). Procedure allowed up to 3 days before D1.

Posttreatment Discontinuation Follow-Up Schedule of Activities

Procedure Category	Protocol Section	Procedure	Posttreatment Discontinuation Follow-Up		Comments
			Study Period		
			Short-Term Follow-Up	Long-Term Follow-Up	
			Visit		

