Attachment 2. Protocol JGDM Clinical Laboratory Tests

All laboratory screening evaluations are to be performed within 14 days prior to enrollment, unless otherwise specified. Eligibility for inclusion in this clinical trial will be based on local clinical laboratory results (not transcribed onto electronic case report forms); duplicate samples will be submitted to the central laboratory. Treatment decisions may be based upon results of tests performed locally. Discrepancies between local and central laboratory that may have an impact on eligibility or treatment decisions will not be considered protocol deviations. On-study clinical laboratory tests assayed for patient safety (such as hematology, serum chemistry, coagulation, and pregnancy tests) are to be collected prior to study treatment.

Clinical Laboratory Tests**Hematology^{a,b}**

Hemoglobin
 Hematocrit
 Erythrocyte count (RBC)
 Mean cell volume
 Mean cell hemoglobin concentration
 Leukocytes (WBC)
 Neutrophils
 Lymphocytes
 Monocytes
 Eosinophils
 Basophils
 Platelets

Coagulation Test^a

Prothrombin time (PT)
 Partial Thromboplastin Time (PTT)
 International normalized ratio (INR)

Urinalysis^{a,c}

Specific gravity
 pH
 Protein
 Glucose
 Ketones
 Blood

Urine leukocyte esterase

Other^d

Immunogenicity samples
 PK samples
 Biomarker samples

Clinical Chemistry^{a,b}**Serum Concentrations of the following:**

Sodium
 Potassium
 Total bilirubin
 Alkaline phosphatase
 Alanine aminotransferase (ALT)
 Aspartate aminotransferase (AST)
 Blood urea nitrogen (BUN)
 Creatinine
 Uric acid
 Calcium
 Glucose, random
 Albumin
 Total protein
 Chloride
 Thyroid-stimulating hormone
 Direct bilirubin

Pregnancy test^{a,c}**Follicle-stimulating hormone (FSH)^{a,f}**

Abbreviations: CRP = clinical research physician; D = Day; PK = pharmacokinetics; RBC = red blood cells; WBC = white blood cells

- a Assayed by local or investigator-designated laboratory.
- b Duplicate samples will also be assayed by a sponsor-designated laboratory.
- c If urinary protein is $\geq 2+$ at evaluations, a 24-hour urine collection (to assess protein) must be collected and must be ≤ 1000 mg of protein in 24 hours (up to 3 business days is allowed if the weekend).
- d Assayed by a sponsor-designated (central) laboratory.

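### The Day 8 blood count may be drawn up to 7 days early, so in Cycles 2-7 it can predate that cycle's doxorubicin and leave the Day 8 ANC rule untested

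*Protocol*

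**What the plan says.** **The dosing rule.** Protocol Section 7.2.3.1 states that "in order to administer single-agent olaratumab on Day 8, ANC must be" at least 750/µL. A lower count delays the dose by up to 7 days, and the dose is skipped if the count has not recovered by then. The section does not say how recent the sample must be. The same section requires ANC of at least 1000/µL to start the next cycle, and Section 7.2.3.1.2.1 withholds doxorubicin below that level.

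**The sampling window.** The on-treatment schedule in Attachment 1 marks hematology on Day 1 and Day 8 of every cycle. Its comment reads "Laboratory assessments may be done within 7 days prior to D1 and D8 of each cycle", one window for both visits.

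**Other timing text.**
- The schedule's column header gives a general ±3 days around the visit day.
- Footnote b reads "Procedure allowed up to 3 days before D1" and names D1 only.
- Footnote a puts procedures before study drug on the treatment day. Attachment 2 says safety laboratory tests "are to be collected prior to study treatment".
- Section 7.2.3.1 ties sample timing to the date olaratumab was actually given.

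**The treatment.** Table JGDM.1 gives doxorubicin 75 mg/m² on Day 1 of Cycles 2-7 and none in Cycle 1.

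**The concern.** The Day 8 rule is a safety check between doxorubicin and the second olaratumab dose of the cycle. It can do that only if the count reflects the marrow after doxorubicin. A 7-day look-back from Day 8 reaches Day 1, where the sample can still precede doxorubicin.

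Three things are at stake.

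- **The dosing decision.** A Day 8 dose could be cleared on a count that carries no information about neutropenia caused by that cycle's doxorubicin.
- **Detection.** Hematology is scheduled only on Days 1 and 8, so the Day 8 count is the only scheduled mid-cycle look. The doxorubicin dose-reduction rule acts on, among other events, "Grade 4 neutropenia without fever lasting more than 1 week", and it needs counts to act on. Section 5.4 reports that in the earlier randomized study "an increase in neutropenia and mucositis, but not in neutropenic sepsis or febrile neutropenia, was observed for olaratumab plus doxorubicin" compared with doxorubicin alone.
- **Safety reporting.** SAP Section 5.11.3 tabulates shifts to the worst postbaseline laboratory grade. A Day 8 value drawn before doxorubicin could understate the worst neutropenia grade.

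The separate Day 1 and Day 8 marks imply two draws. The schedule does not tell sites to reuse one sample; the gap is that the second draw may be this early.

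**Working it through.** The plan gives no figure to reproduce. The check is calendar arithmetic plus a comparison of thresholds.

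**Inputs**
- Hematology window: 7 days before Day 8 (Attachment 1).
- Doxorubicin: Day 1 of Cycles 2-7, with a 21-day cycle (Table JGDM.1).
- ANC thresholds: at least 1000/µL to start a cycle, at least 750/µL for Day 8 olaratumab (Section 7.2.3.1).
- Visit window: ±3 days (Attachment 1 column header).

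**1. Earliest compliant draw.** Earliest day = day of the Day 8 dose − 7, counting from the actual dose as Section 7.2.3.1 directs.

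| Day 8 dose given on | Window opens | Day 1 pre-dose sample allowed? |
|---|---|---|
| Day 5 | 3 days before Day 1 | Yes |
| Day 6 | 2 days before Day 1 | Yes |
| Day 7 | 1 day before Day 1 | Yes |
| Day 8 | Day 1 | Yes |
| Day 9 | Day 2 | No |
| Day 10 | Day 3 | No |
| Day 11 | Day 4 | No |

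The gap exists for on-schedule and early dosing. It closes from Day 9 onward.

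**2. What a Day 1 count can show.** If the Day 1 count is the one that cleared the cycle, it is at least 1000/µL. Since 1000 > 750, it passes the Day 8 rule automatically, and no delay or skip can follow. If it is a separate pre-dose draw, that implication is not strict, but the sample still precedes doxorubicin.

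**3. Time without a scheduled count.** Next Day 1 = Day 22 of an undelayed cycle. Its window opens on Day 22 − 7 = Day 15. If the Day 8 sample is taken on Day 1, the gap after doxorubicin is 15 − 1 = 14 days to 22 − 1 = 21 days.

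**4. Shorter windows, dose on Day 8.**

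| Window | Earliest draw | Days after doxorubicin |
|---|---|---|
| 7 days (current) | Day 1 | 0 |
| 3 days | Day 5 | 4 |
| 2 days | Day 6 | 5 |
| 1 day | Day 7 | 6 |

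**5. Early visits under a 3-day window.** A Day 8 visit held on Day 5 could use a sample from 5 − 3 = Day 2, which is after doxorubicin but only by one day.

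**6. Decisions exposed.** Cycles 2 to 7 give at most 6 Day 8 decisions per patient. Cycle 1 gives none, because it has no doxorubicin.

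**7. Does other text close the gap?** Footnote b limits D1 only. Footnote a and Attachment 2 require collection before treatment, which a Day 1 pre-dose sample satisfies. The ±3-day header would put the draw no earlier than Day 5, but the hematology comment is specific to this test and wider, so it is the better guide to what is allowed.

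**The case against.** The strongest reply is that nobody would read the protocol this way. Section 7.2.3.1 speaks of the ANC in the present tense and provides for waiting until it recovers, which points to a current count. The Attachment 1 comment is permissive logistics text. Patients attend on Day 8 anyway for weight, examination, vital signs, toxicity assessment and infusion, so there is little reason to draw the count a week early. The ±3-day header can also be read as the limit.

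The likely practice may well be a draw near Day 8, and how often a site would do otherwise is unknown. But intent is not a requirement. If the header is taken to override the comment, the protocol holds two conflicting windows for a test that gates dosing, which also needs correcting.

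A second reply is that the exposure is limited. Day 8 is olaratumab alone, and Section 7.2.3.1 says olaratumab need not be altered for doxorubicin toxicity. The next doxorubicin dose has its own ANC threshold, G-CSF is allowed, and the sponsor reviews safety after the first 5 patients complete Cycle 2. One Day 8 count cannot establish neutropenia lasting more than a week, and the documents give no timing for the nadir. All of this stands and bounds the consequence. It does not remove the point: the Day 8 ANC threshold is stated without regard to cause, and neither the Day 8 examination nor G-CSF use measures ANC.

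**Conclusion.** The concern holds. As written, a compliant Day 8 count in Cycles 2-7 can precede that cycle's doxorubicin, and the Day 8 ANC rule then tests nothing about the effect of that dose.

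The size is at most six decisions per patient, with 14 to 21 days after doxorubicin lacking a scheduled count when the early draw is used. This rests on three assumptions: the hematology comment governs over the general column header, the Day 8 dose is given on Day 8 or earlier in its window, and the cycle is not delayed. The actual frequency cannot be estimated from the documents, so confidence in the practical consequence is medium.

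This is a patient-safety and safety-data matter. It does not touch the sample size or the comparison before and after Cycle 1. It should be corrected because one instruction lets sites bypass another and the correction is cheap.

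**What to change.** Amend the hematology comment in Attachment 1 along these lines: the 7-day window applies to Day 1 only; the Day 8 ANC must be drawn after that cycle's Day 1 dosing and no more than 3 days before the actual Day 8 olaratumab dose; if that dose is delayed, the interval runs back from the date it is given.

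Three days is an example, consistent with windows used elsewhere in the schedule, such as "Mandatory PET scan must be collected up to 3 days prior to the first dose of C2D1". It is not derived from a nadir argument, so the clinical team should confirm the interval. They should also decide whether a visit held as early as Day 5 needs a same-day count.

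The cost is one line. No sample is added, because Day 8 hematology is already scheduled in every cycle. Sites lose some scheduling flexibility: for a visit on Day 8, permitted draw days narrow from Days 1-8 to Days 5-8.
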